7.3 ADVERSE EVENTS, INCIDENTAL FINDINGS, AND OTHER POTENTIAL ISSUES

Please see the HRP 503 form section **4. Provisions for Research Related Harm/Injury → Incidental Findings and Other Potential Issues** and **Provisions for Research Related Harm / Injury** for details on the procedures the research team will implement to handle and report adverse events, incidental findings, and other potential issues.

8 STATISTICAL CONSIDERATIONS

8.1 DATA ANALYSIS PLAN (INCLUDING ANY STATISTICAL PROCEDURES)

8.1.1 HYPOTHESIS TESTING

Hypothesis 1.1) BN in the fed relative to fasted state will demonstrate impaired performance and deficient frontostriatal activation when inhibiting responses, whereas HC will show the opposite pattern. Behavioral analyses will examine state-dependent group differences in stop signal reaction time and % correct stop trials. Neuroimaging analyses will examine the impact of eating on activation during successful inhibition, regardless of the anticipated probability of the upcoming need to stop (P(stop)). Linear mixed effects (LME) models will be used for both sets of analyses.

Hypothesis 1.2) In BN, frontostriatal signals for the anticipated need to stop (P(stop)) and inhibitory prediction errors will be reduced in the fed relative to fasted state. HC will show the opposite pattern. Group x Visit x Trial Type LME analyses will examine how eating impacts group differences in P(stop)-modulated inhibitory activation (i.e., activation during Stop versus Go trials) and group differences in P(stop) activation, regardless of trial type. Group x Visit LME analyses will examine how eating impacts group differences in signed and unsigned prediction errors. We will examine both signed and unsigned prediction errors as each may provide unique information to inform behavioral adjustment: Unsigned prediction errors capture the overall mismatch between one's internal model of prediction and the actual outcome, whereas signed prediction

The Influences of Eating and Fasting on Inhibitory Control in Bulimia Nervosa: A Computational Neuroimaging Study

STUDY-19-00591

v.05.10.2023

errors provide additional information about the directionality of this mismatch, which may bias an individual to be more or less cautious (i.e., oriented more toward stopping or going).

Hypotheses 2.1 & 2.2) More severe binge eating and purging will be associated with lower frontostriatal signals for P(stop) and inhibitory prediction errors in the fed vs. fasted state; more severe dietary restriction will be associated with increased frontostriatal signals for P(stop) and prediction errors in the fasted vs. fed state. Within the BN group, Symptom Severity x Visit generalized LMEs will test how eating impacts the relations between self-report measures (binge eating, purging, and fasting frequencies) and activation associated with each neurocomputational regressor of interest. We will examine whether areas from this analysis overlap with clusters identified in Aim 1 to assess the potential contribution of illness severity to group differences in activation.

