1.2 SCHEMA

Phone Screen

Total N = 500 per PPHS' definition of enrollment); N = 60 (per NIH's definition of enrollment)

Phone screen e-consenting process, phone screen potential participants by inclusion and exclusion criteria

Next Screening

Conduct full study e-consenting process, remote or in-person clinical interviews and in-person pre-scan screening and assessment; if eligible, schedule fMRI scanning visits

Participants with
Bulimia Nervosa
n = 30

Participants without
Bulimia Nervosa
n = 30

Online self-report questionnaires

Randomization
(Participants are randomly assigned (in even numbers across the two groups) to fMRI scan order)

fMRI Scan Visit 1

Fasted State:
16 hours of fasting, fMRI scan

Fed State:
Fed a standardized meal, fMRI scan

fMRI Scan Visit 2

Fed State:
Fed a standardized meal, fMRI scan

Fasted State:
16 hours of fasting, fMRI scan

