- Positive and Negative Affect Schedule (PANAS)
- Spielberger State-Trait Anxiety Inventory (STAI-S)
- State Difficulties in Emotion Regulation Scale (S-DERS)

Information collected will be examined in correlation with behavioral performance and neural responses to decision-making tasks. Subjects will perform an inhibitory control task and two decision-making tasks at both scanning study visits. During the scan, visual stimuli are projected from a computer onto a screen in the scan room, and participants hear auditory stimuli via headphones and log their responses to visual and auditory stimuli using a button response box for both tasks. The remainder of scan time consists of structural sequences and resting state sequences during which the subject is asked to lie still and stay awake. A fixation cross is displayed during this portion. The imaging procedure involves lying quietly on a table for approximately 1.5 hours. No pain or discomfort results from this procedure.

On both scan days, participants will be offered a granola bar snack after scanning is complete.

At the conclusion of study participation, we will provide a customized written set of referrals, which includes low-fee, full-fee, and insurance-based options that include both Mount Sinai and external treatment sources. We are available to discuss follow-up with any of these options and communicate this availability to participants. However, as we are not providing treatment in this study, we will not engage in formal case management for participants.

During these cognitive tasks, participants will have the opportunity to earn a bonus between \$0 and \$15. Monetary bonuses are a common technique in behavioral economics that help to ensure that participants' behavior is ecologically valid and as true to life as possible. It also helps to minimize the risk of boredom and fatigue that participants will face when playing these games. Depending on the task, these bonuses are either calculated based upon a cumulative score, meaning participants bank up small rewards over the course of the task, or they receive the full payout from a randomly selected trial. The full details for how these bonuses are calculated is made clear to the participants in the instruction screens of the individual tasks.

7.2 DESCRIPTION OF THE SOURCE RECORDS THAT WILL BE USED TO COLLECT DATA ABOUT SUBJECTS

Names of Standardized Instruments (Psychiatric Measures):

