8.1.2 EXPLORATORY ANALYSES AND POTENTIAL CONFOUNDS

- 1) Resting CBF: ASL data will be subjected to Group x Visit LMEs a) restricted to masks of Aim 1 LME results and b) across the whole brain. If whole-brain mean CBF differences are observed, Aim 1 analyses will be repeated covarying for CBF. However, localized differences in CBF that overlap with Aim 1 results will further inform BOLD signal interpretation.
- 2) Illness Duration: We will test the association between months with BN and neural measures of interest.
- 3) BN Comorbidity and Treatment: Depending on final sample composition, post-hoc tests will examine a) group differences controlling for MDD, GAD, and SAD b) group differences excluding comorbid MDD, GAD, and SAD or c) associations of PHQ-9 and STAI-T scores with group differences in activation. Potentially confounding effects of treatment-seeking status will be evaluated in a similar manner.
- 4) Additional Measures of BN Symptom Severity and State Emotion/Arousal: Analyses described for Hypotheses 2.1 and 2.2 will be repeated using the pre-scan state measures.
- 5) Functional Connectivity: Psychophysiological interaction analyses will interrogate state-specific frontostriatal connectivity during stop-signal inhibition.
- 6) We will explore group differences in performance and/or brain activation during the other decision-making neurocognitive tasks and associations of these measures with BN clinical symptoms.

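### Scan order is randomised, but no mixed model with listed terms includes session or order, so any first-to-second-scan effect would inflate standard errors and cost power on the fed-fasted tests

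*Combined protocol and SAP*

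**What the plan says.** **Design.** The schema (section 1.2) states: "Participants are randomly assigned (in even numbers across the two groups) to fMRI scan order". Sections 3.1 and 7.1 describe the two scans as counterbalanced, and section 7.1 puts them at most a week apart. It also says: "Subjects will perform an inhibitory control task and two decision-making tasks at both scanning study visits".

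**Models with listed terms (sections 8.1.1 and 8.1.2).**
- P(stop), Hypothesis 1.2: "Group x Visit x Trial Type LME analyses will examine how eating impacts group differences in P(stop)-modulated inhibitory activation". The same model also covers "group differences in P(stop) activation, regardless of trial type".
- Prediction errors, Hypothesis 1.2: "Group x Visit LME analyses will examine how eating impacts group differences in signed and unsigned prediction errors".
- Aim 2, BN group only: "Symptom Severity x Visit generalized LMEs will test how eating impacts the relations between self-report measures".
- Resting blood flow: "ASL data will be subjected to Group x Visit LMEs".

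Hypothesis 1.1 is assigned mixed models without a list of terms.

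**Adjustments named.** Section 8.1.2, on potential confounds, includes a conditional step in which "Aim 1 analyses will be repeated covarying for CBF". It also covers comorbidity, treatment-seeking and illness duration. Session and scan order are not on the list.

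**Power.** Section 8.2 reports over 80% power for a three-way interaction of d = .80 with 30 women per group and two-sided alpha .05. It mentions no session effect in the simulation.

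**The concern.** Repeating a task in a scanner within a week can produce a first-to-second-scan change through practice or familiarity. The design guards against this by randomising order, but the models as listed do not take order into account. In them, Visit carries the fed-fasted contrast, since they are said to test the effect of eating. The schema uses Visit 1 and Visit 2 for first and second scan. No listed term therefore represents session.

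With balanced order the session effect is orthogonal to state, and the group comparison of the fed-fasted change is not biased. The omitted effect still adds a positive amount to that difference for women in one order and a negative amount for women in the other. The model reads this as noise, so standard errors are too large, the Group x State test is conservative and power is lost.

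Aim 2 behaves a little differently. Order is not balanced over symptom severity, so chance imbalance makes the slope estimate itself noisier. The test keeps its 5% level but has less power.

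For Hypothesis 1.1 the point is only that session adjustment is not stated.

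**Working it through.** **Inputs from the documents:** 30 per group, d = .80, two-sided alpha .05 (section 8.2), and order allocated evenly (section 1.2), taken here as 15 per order in each group.

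**Assumptions:** the session effect *s* (second minus first scan), in SDs of the difference being tested, at 0, .25, .5 and .75; d = .80 also for the two-way Group x State test, since the plan gives that value only for the three-way interaction; a severity correlation of .5 in Aim 2; complete pairs.

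**Step 1: the plan's figure.** Treat the interaction as a two-group comparison of one within-woman contrast with SD 1. The SE is √(2/30) = 0.258 and .80/0.258 = 3.10. Power is 86.1% (noncentral t) or 87.3% (normal), consistent with over 80%.

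**Step 2: Group x State.** For each woman, fed minus fasted = d × group ± *s* + error of SD 1, with the sign set by order. Leaving order out multiplies the reported SE by about √(1 + *s*²). At *s* = .5 this is √1.25 = 1.12. Simulation (200,000 replicates):

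| *s* | Power without Session | Power with Session | Mean reported SE without Session | Null rejection without Session |
|---|---|---|---|---|
| 0 | 0.86 | 0.86 | 0.257 | 4.9% |
| .25 | 0.85 | 0.86 | 0.265 | 4.3% |
| .5 | 0.80 | 0.86 | 0.288 | 2.8% |
| .75 | 0.72 | 0.86 | 0.324 | 1.4% |

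The true SD of the estimate is 0.258 in every row.

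**Step 3: Aim 2, n = 30, r = .5.** The residual variance is 1 − .5² = .75 with Session and .75 + *s*² without it. At *s* = .5 it goes from .75 to 1.00. Simulated power without Session is 0.83, 0.80, 0.72 and 0.60 at the four values of *s*; with Session it is about 0.81 throughout. At *s* = .5, r = .4 gives about 0.50 against 0.60, and r = .6 gives just under 0.9 against 0.95. Null rejection is about 5% either way.

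**Step 4: the three-way test, d = .80.** There are four cells per woman (state by trial type). The result depends on the random effects, which the plan does not state.

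- *Session effect shared by Stop and Go*, in SDs of the trial-averaged fed-fasted difference. It cancels from the three-way contrast. With person-by-state and person-by-trial-type random effects nothing is lost (0.86 against 0.86). With a random intercept only, it enters one of the three within-woman contrasts that are pooled into the error, so the SE grows by about √(1 + *s*²/3). Power is 0.85 against 0.87 at .5 SD, and 0.79 against 0.87 at 1 SD.
- *Session effect that differs between Stop and Go*, .5 SD of the three-way contrast. With the fuller random effects power is 0.80 without a term and 0.86 with Session x Trial Type. With a random intercept only it is 0.85 with no term, 0.85 with Session alone and 0.87 with Session x Trial Type.

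**Step 5: P(stop) regardless of trial type.** This is the Group x State test in the same model, so a shared session effect does not cancel. At *s* = .5, power is 0.80 against 0.86 (fuller random effects) or 0.85 against 0.87 (random intercept only).

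At *s* = .25 every loss in Steps 2 to 5 is 2 points or less.

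**The case against.** The strongest reply is that randomised, counterbalanced order already protects validity, and only optional variance reduction is left. That is right about validity. But when the SE is 12% too large the reported uncertainty is wrong, and the term that corrects it is a factor the study already randomises.

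Second, the harm depends on an effect size the documents do not give. Section 7.1 also has participants practise computerised decision-making tasks before the first scan, which could shrink a learning effect, although the stop-signal task is not named there. This stands: the loss is conditional, and small below about 0.25 SD.

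Third, the study was sized on the three-way test, which is the least exposed, and d = .80 was never planned for the two-way tests. This also stands. The two-way and Aim 2 figures illustrate sensitivity; they do not correct a stated power.

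Fourth, adjustment is not free in Aim 2. With r = .5 the model without Session is slightly better when *s* is below about .2 (0.83 against about 0.81 at *s* = 0). The penalty is one to two points, against nine gained at *s* = .5.

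Fifth, a term left unlisted may still be fitted. That is possible. But section 8.1.2 names the adjustments it intends, and session is not among them.

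**Conclusion.** The concern holds, as a matter of efficiency. No mixed model with listed terms accounts for session or order, although order is randomised. With balanced order there is no bias in the group comparison and no excess of false positives.

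At an assumed session effect of 0.5 SD, the cost is about 6 points of power for Group x State (0.86 to 0.80) and about 9 for Aim 2 (0.81 to 0.72). For the three-way test it ranges from nothing to about 6 points, depending on the unstated random effects and on whether the session effect differs between Stop and Go. These figures rest on d = .80 for the two-way tests, r = .5 in Aim 2, complete pairs and 15 women per order in each group.

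The absence of bias also depends on balance among the women analysed. Suppose, for illustration, that completers split 15/11 by order in BN and 13/15 in controls. The mean order codes are 4/26 = 0.15 and −2/28 = −0.07, so omitting Session would shift the Group x State estimate by about 0.23 × *s*. Including Session removes that shift.

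**What to change.** - Call the fed/fasted factor State, so that it is not confused with first and second visit.
- Add Session (first/second scan) as a fixed effect to every fed-fasted mixed model, including those for Hypothesis 1.1, Aim 2 and resting blood flow.
- In the Group x State x Trial Type model, also add Session x Trial Type. Session alone does not recover a loss that differs between Stop and Go.
- Optionally, write out the random effects, which decide how much the three-way test can lose, and prespecify a Group x Session sensitivity analysis.

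The cost is a few words of text, one degree of freedom (two in the three-way model) and no new data. If there is no session effect, simulated power is unchanged for Group x State (0.861 with or without the term) and falls by one to two points for Aim 2 (0.83 to about 0.81).

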The Influences of Eating and Fasting on Inhibitory Control in Bulimia Nervosa: A Computational Neuroimaging Study

STUDY-19-00591

v.05.10.2023

disinhibiting. This could create a fed-state vulnerability and make it difficult to stop eating after starting.

The overarching hypothesis of this research study is that in BN, frontostriatal function and inhibitory control are enhanced in the fasted state, but impaired in the fed state. This study proposes that this aberrant state-dependent activation promotes prolonged periods of dietary restriction punctuated by out-of-control binge/purge episodes. To test this hypothesis, this project will compare neural responses of 30 women with BN to 30 group-matched healthy controls (HC) at two counterbalanced scans (after a 16-h fast and after a standardized meal) using Bayesian ideal observer modeling of stop-signal task inhibition. To assess the clinical significance of metabolic-state sensitivity, this project will examine associations of neural response with symptom severity. This project will serve as a vehicle for formal training and mentorship in repeated-measures neuroimaging methodology and analysis, computational modeling in psychiatry, and the neurobiology of BN symptoms. Characterizing the influences of eating and fasting on the control-related dysfunction that may contribute to maladaptive BN symptoms is critical to developing precise pathophysiological models and more accurate and effective treatments.

Aim 1: To determine whether eating and fasting abnormally interfere with the capacity of individuals with BN to adaptively exert inhibitory control

Hypothesis 1.1: Women with BN in the fed relative to fasted state will demonstrate impaired performance and deficient frontostriatal activation when inhibiting responses, whereas HC will show the opposite pattern. Hypothesis 1.2: In BN, frontostriatal signals for the trial-level anticipated need to stop ($P(\text{stop})$) and Bayesian prediction errors will be reduced in the fed relative to fasted state. HC will show the opposite pattern. Associated Training: Goal 1: To develop expertise in repeated-measures neuroimaging and analysis, including measurement of potential state-based fMRI normalization factors (e.g., resting perfusion); Goal 2: To learn to independently conduct computational model-based analysis of fMRI data in eating disorders

Aim 2: To identify associations of BN symptom severity with state-specific frontostriatal activation

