8.2 POWER ANALYSIS (SAMPLE SIZE DETERMINATION)

Our sample size was selected based on the most rigorous analysis of our primary outcome measure (a Group x Visit x Trial Type LME). FMRI studies using inhibitory control tasks report large BN vs. HC effect sizes (mean striatum $d = .82$; mean PFC $d = .96$),^{62, 167} and our pilot data from remitted BN and HC suggest a large Group x Visit x Inhibitory Difficulty interaction in the DLPFC ($d = .83$). Prior work using the proposed Bayesian models to study substance dependence report large Group x P(stop)-modulated Trial Type (Stop*P(stop), Go*P(stop)) interactions in the DLPFC ($d = .90$) and caudate ($d = .81$).²⁰ Based on these prior data, we expect large Group x Visit x Trial Type frontostriatal interactions. Using computed Stop*P(stop) and Go*P(stop) regressors from the DLPFC and caudate from this prior study of substance dependence, we determined beta estimates were normally distributed with homogeneous variance across groups. We simulated 1,000 datasets with a 3-way interaction (Group x Visit x

Trial Type) and fitted a mixed effects model to each dataset; power to detect a large ($d = .80$) 3-way interaction with 30 women per group was estimated at over 80% with two-sided alpha =.05.

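### Map overlap is the stated way to judge whether illness severity contributes to group differences, but it has no threshold, criterion or error rate, and its absence tells little with 30 BN women

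*Combined protocol and SAP*

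**What the plan says.** Section 8.1.1 tests Hypotheses 2.1 and 2.2 with a model: "Within the BN group, Symptom Severity x Visit generalized LMEs will test how eating impacts the relations" between three self-reported frequencies (binge eating, purging, fasting) and "activation associated with each neurocomputational regressor of interest". A single further sentence connects that result to Aim 1: "We will examine whether areas from this analysis overlap with clusters identified in Aim 1 to assess the potential contribution of illness severity" to the differences between groups.

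Neither Section 8.1.1 nor any other section gives a voxel or cluster threshold, a minimum extent of overlap, a reference for chance overlap, or a multiplicity rule. The only power statement, in Section 8.2, is for Aim 1: "power to detect a large ($d = .80$) 3-way interaction with 30 women per group" is put at over 80%, "with two-sided alpha =.05". No power is stated for Aim 2.

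Section 8.1.2 (item 1) runs the cerebral blood flow models inside masks taken from the Aim 1 results. No such restriction is stated for the severity models.

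**The concern.** Two significance maps can fail to overlap merely because one of them missed its threshold at that location. They can overlap by chance, at a rate set by thresholds and rules that the plan leaves open. When they do overlap, the map does not say how strongly severity relates to the signal there.

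Section 4.1 presents Aim 2 as the assessment of the clinical significance of the state effects. The severity models show whether severity relates to the signal somewhere. Whether it does so where the groups differ is left to the overlap step, so the step that joins the two aims has no operating characteristics.

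**Working it through.** **Inputs.** From the documents: 30 BN women and 30 controls (Section 3.1); severity models within BN only (Section 8.1.1); d = .80 and two-sided alpha .05 (Section 8.2); three severity measures (Section 8.1.1). Section 8.1.1 implies at least three neural regressors: P(stop), signed prediction error and unsigned prediction error. Assumed, because the documents give neither: a severity association of r = .3 to .5, and voxel thresholds of p<.05, .005 and .001.

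**1. The plan's own figure.** Take d as standardised on the per-participant interaction contrast; the plan does not give its variance inputs. The noncentrality is d × √(n/2) = .80 × √15 = 3.10 with 58 df. Two-sided power is 86% at .05, consistent with the stated figure of over 80%. At the same d it is 57% at .005 and 37% at .001.

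**2. Severity effect at one location.** By Fisher z, power ≈ Φ(atanh(r) × √(n−3) − z for 1−α/2), with √27 = 5.196. For r = .5, atanh(.5) × 5.196 = 2.854. At p<.005 the critical value is 2.807, giving Φ(0.047) = 52%. At p<.001 it is 3.291, giving Φ(−0.437) = 33%.

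**3. Both maps significant at the same location.** Multiply the results of steps 1 and 2, for example .519 × .574 = .298 and .046 × .369 = .017.

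| r | Severity alone, p<.05 / .005 / .001 | Both maps, p<.05 / .005 / .001 |
|---|---|---|
| .3 | 36% / 12% / 5% | 31% / 7% / 2% |
| .4 | 60% / 27% / 14% | 51% / 16% / 5% |
| .5 | 81% / 52% / 33% | 70% / 30% / 12% |

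A simulation of 40,000 studies agreed closely: for r = .5, both maps were significant in 29% at p<.005 and 11% at p<.001.

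**4. Dependence on the unstated rule.** This is an illustration only: 400 runs of a smooth three-dimensional field with a true Aim 1 effect over 360 voxels.

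- With no severity link, at least one voxel overlapped in 98%, 18% and 4% of runs at p<.05, .005 and .001.
- With a real link across the whole region at p<.001, at least one voxel overlapped in 41%, 70% and 88% of runs for r = .3, .4 and .5.
- Requiring at least 20 shared voxels cut those three figures to 7%, 26% and 52%.

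**5. The direct alternative.** One test of the slope in a cluster at .05 has 36%, 60% and 81% power for r = .3, .4 and .5. Bonferroni over three measures (alpha .0167, critical value 2.394) gives Φ(2.854 − 2.394) = 68% at r = .5. Over 3 × 3 = 9 tests (alpha .0056, critical value 2.773) it gives Φ(2.854 − 2.773) = 53%. Uncorrected, nine independent tests carry a 1 − .95⁹ = 37% chance of at least one false positive.

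**6. Circularity.** Under normality the within-BN slope is independent of the BN-versus-control mean difference. In the simulation with r = 0, Aim 1 was significant in .859 of studies and both tests in .043. The slope's false-positive rate given a significant Aim 1 result is therefore .043/.859 = 5%, so testing slopes inside Aim 1 clusters does not inflate it.

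**The case against.** The strongest reply is that the overlap sentence is a cautious follow-up and not the test of Aim 2. The severity models test Hypotheses 2.1 and 2.2 directly and yield slopes, and Section 8.1.2 adds illness-duration and pre-scan state analyses. This stands, and it limits the point to the one step that relates severity to the Aim 1 clusters.

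Three stronger readings are tempting, and the documents do not support them.

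- A reader might infer that overlap will usually be absent at this sample size even when the link is real. That depends on a threshold and rule the plan does not state. At p<.05, joint detection at one location passes 50% once r reaches about .39. If any shared voxel counts, the illustration shows overlap in 88% of runs at r = .5 and p<.001.
- A reader might infer that a cluster-level test raises power from about a third to over 80%. That sets alpha .001 against an uncorrected .05. After correction over nine tests the figure is 53%, about the same as a voxel at p<.005 (52%).
- A reader might infer that a lack of overlap will be reported as severity not mattering. The plan does not say so, and its wording is exploratory.

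None of this supplies an error rate or an effect size for the overlap step.

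**Conclusion.** The point holds in limited form. Overlap is the stated means of judging severity's contribution to group differences, and it has no threshold, criterion or error rate and gives no effect size. With 30 BN women its absence is uninformative: at p<.005 to p<.001, a real r of .3 to .5 would be significant in both maps at a given location in about 2% to 30% of studies. That range rests on the assumed r and thresholds, on d = .80 applying to the per-participant contrast, and on looking at one location; counting any shared voxel in a region raises it.

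The case for changing the method is a defined error rate and an interpretable estimate, more than a gain in power. No primary analysis is affected. This is a cheap improvement.

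**What to change.** In Section 8.1.1, replace the overlap criterion with estimation inside the Aim 1 clusters:

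- For each cluster, extract each BN participant's fed-minus-fasted value of the contrast that defined it. For Group x Visit x Trial Type clusters this is the Stop-minus-Go P(stop)-modulated beta; for Group x Visit clusters it is the P(stop) or prediction-error beta. A plain cluster mean would lose the Stop-versus-Go contrast.
- Estimate the slope on each of the three severity measures and report it with a 95% confidence interval, whether or not it is significant.
- State a multiplicity rule over measures, regressors and clusters, or label the slopes as supportive.
- Keep the overlap map as description only, and state the thresholds used to draw it.

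The cost is plan wording, extraction of cluster values and a set of regressions, with no new data collection. Masking by Aim 1 results is already planned for cerebral blood flow. The downside is a modest number of extra secondary tests with limited power after correction, so the intervals should carry the interpretation.
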